1. BACKGROUND

Nutropin [somatropin (rDNA origin) for injection] is a lyophilized form of human growth hormone (hGH) produced by recombinant DNA technology. Nutropin AQ is a liquid formulation with the chemical structure of somatropin identical to lyophilized Nutropin.

To use the most advanced methodology and equipment to ensure a continued supply of Nutropin AQ, Genentech has updated its manufacturing process while continuing to use the same *Escherichia coli* growth hormone production system. Chemical and biological characterization (including potency) has demonstrated comparability of drug substance produced by the original and updated manufacturing processes and, based on this, the new manufacturing process that is used to produce Nutropin AQ v1.1 has been approved by FDA.

This study, performed in children with growth hormone deficiency (GHD), will assess the safety and immunogenicity profile of Nutropin AQ produced by the new manufacturing process.

For further background information please see Section 1 of the protocol.

This Statistical Analysis Plan (SAP) describes the statistical methods to be used for study ML29543. This version of the SAP has been developed using version 2 of the study protocol dated 22 April 2015 and revision 1.2 of the CRF dated 26 July 2017.

2. STUDY DESIGN

This is a Phase IV, multicenter, open-label, single-arm study of somatropin (rDNA origin) (Nutropin AQ v1.1) in naïve prepubertal children with GHD. Approximately 80 patients will be enrolled at approximately 30 sites in the U.S. and will be treated with daily subcutaneous (SC) injections of Nutropin AQ v1.1 at a dose of up to 0.043 mg/kg/day (0.3 mg/kg/week, which is the approved and indicated dosage for pediatric GHD; refer to the U.S. Prescribing Information [USPI] for Nutropin AQ) for 12 months. Dose adjustments may be made at the Month 6 visit for changes in weight and insulin growth factor-1 (IGF-1) levels, if measured.

2.1 PROTOCOL SYNOPSIS

The Protocol Synopsis is in Appendix 1. For additional details, see the Schedule of Assessments in Appendix 2.

2.2 OUTCOME MEASURES

2.2.1 Primary Outcome Measures

• The primary outcome measure for this study is the occurrence of anti-GH antibodies in rhGH-naïve, prepubertal GHD children treated with Nutropin AQ v1.1.

Nutropin AQ (Somatropin [rDNA origin])—Genentech, Inc. 4/Statistical Analysis Plan ML29543

2.2.2 Secondary Outcome Measures

• The occurrence of functional growth attenuation in association with positive antibody formation in patients treated with Nutropin AQ v1.1

This will be considered in any patient who demonstrates an initial growth response greater than pretreatment velocity after treatment with Nutropin AQ v1.1, but then slows to below pretreatment velocity in the ensuing 6- to 12-month period (or reaches ≤2 cm per year)

- The difference between the annualized 6- and 12-month growth velocities for patients who were anti-GH antibody-positive at any post-baseline visit and those who were anti-GH antibody-negative at all visits (including baseline)
- The formation of neutralizing antibodies, and the association between the presence of neutralizing anti-GH antibodies and growth attenuation.

2.2.3 Exploratory Efficacy Outcome Measures

This section is not applicable.

2.2.4 Pharmacokinetic Efficacy Outcome Measures

This section is not applicable.

2.2.5 Safety Outcome Measures

No specific safety assessments are planned for this study. However, analysis of all safety events will be performed.

2.3 DETERMINATION OF SAMPLE SIZE

A target enrollment of 80 patients was chosen to allow for a projected 10–15% dropout rate and exclusion of growth data for an estimated 10% of patients who might enter puberty during the study period and leave sufficient patient numbers to compare to previous studies of immunogenicity. This target enrollment was based on enrollment in a previous study (L0368) which planned to enroll 60 patients for the assessment of growth rate and change in height standard deviation score (SDS). An initial sample size was chosen to ensure that at least 50 patients would complete the study (L0368 FR 30SEP97; Sec 4.8.4).

This study is expected to yield a minimum of 50 evaluable patients. Given a sample size of 50, and an assumed 50% of patients developing anti-GH antibodies, the 95% confidence interval (CI) around this proportion will be (35.53%, 64.47%). This interval was calculated using Clopper-Pearson methodology. Fluctuations in the proportion of patients developing anti-GH antibodies and the increase of evaluable patients will result in more precise confidence intervals. The exact confidence intervals for the scenarios for sample size of 50 and 60 in combination with the proportion of patients who are anti-GH antibody positive of 50% and 20% are listed in Table 1.

Nutropin AQ (Somatropin [rDNA origin])—Genentech, Inc. 5/Statistical Analysis Plan ML29543

Table 1

N	Proportion of Patients Who Are Anti-GH Antibody Positive	95% Confidence Interval (Lower Limit)	95% Confidence Interval (Upper Limit)
50	0.5	0.3553	0.6447
60	0.5	0.3681	0.6319
50	0.2	0.1003	0.3372
60	0.2	0.1078	0.3230

Clopper-Pearson 95% Confidence Intervals for the Proportion of Patients Who Are Anti-GH Antibody Positive Based on 50 and 60 Patients

2.4 ANALYSIS TIMING

No interim analysis is planned. The final analysis will be performed after the completion of the study and after the clinical database is locked.

3. STUDY CONDUCT

3.1 RANDOMIZATION ISSUES

There is no randomization for this open-label, single arm study.

3.2 INDEPENDENT REVIEW FACILITY

This section is not applicable.

3.3 DATA MONITORING

There is no independent data monitoring committee planned for this study.

4. STATISTICAL METHODS

Data listings will be produced for all endpoints. Descriptive statistics and graphic displays will be provided to summarize data from this study. There are no formal statistical hypothesis tests planned.

Categorical variables will be summarized as the number and percentage of patients or occurrences in each response category. Continuous variables will be summarized using descriptive statistics (number of observations, mean, standard deviation, median, minimum and maximum).

4.1 ANALYSIS POPULATIONS

There are three analysis populations for this study: Intent-to-treat (ITT), Safety and Modified ITT.

4.1.1 Intent-to-Treat (ITT) Population

The ITT Population includes all patients enrolled in the study.

Nutropin AQ (Somatropin [rDNA origin])—Genentech, Inc. 6/Statistical Analysis Plan ML29543

4.1.2 Per Protocol Population

This section is not applicable.

4.1.3 Pharmacokinetic-Evaluable Population

This section is not applicable.

4.1.4 Safety Population

The Safety Population includes all enrolled patients (i.e. ITT population) who received at least one dose of study drug.

4.1.5 Modified Intent-to-Treat (mITT) Population

The Modified ITT Population includes all enrolled patients (i.e. ITT population) who received at least one dose of study drug and had at least one post-baseline assessment (e.g., lab, vital signs, physical exam, concomitant medication, and adverse event).

4.2 ANALYSIS OF STUDY CONDUCT

The number and percentage of patients who have signed informed consent, met eligibility criteria, had major protocol deviations, and received treatment will be tabulated. Reasons for not completing the study will also be tabulated using numbers and percentages.

A summary of the duration of the patient participation in the study will be produced. Duration will be calculated as the date of the last study assessment minus the first study drug administration date + 1.

The number and percentage of patients included and excluded from the analysis populations will be tabulated. Reason(s) for exclusion from each population will be similarly summarized.

4.3 ANALYSIS OF TREATMENT GROUP COMPARABILITY

This is a single-arm study therefore only descriptive statistics will be provided; no treatment group comparison will be performed.

Clinically important demographic and disease characteristics at baseline will be summarized overall. Summaries will be produced for the ITT population.

Continuous variables will be summarized by the number of non-missing observations, mean, standard deviation, median, minimum and maximum values. Categorical variables will be summarized using numbers and percentages of patients in each category; unknown or missing will be included as a separate category.

The variables to be summarized include but are not limited to the following:

• Demographics: sex, ethnicity, race(s), age (continuous).

Nutropin AQ (Somatropin [rDNA origin])—Genentech, Inc. 7/Statistical Analysis Plan ML29543 Baseline characteristics: height, weight, height standard deviation score (SDS) (continuous and categorized as ≤ -3, >-3 to ≤ -2, >-2 to ≤ -1, >-1), pre-treatment growth velocity, and prepubertal Tanner stage < 1 (yes or no). See Appendix 3 for the SAS macros for the calculation of normal height SDS (z-scores) for this study.

Pre-treatment growth velocity is calculated from the baseline and last historical height measurements as: 365.25 × (Baseline height – last historical height)/(date of baseline height – date of last historical height)

- Disease-related characteristics: birth weight, bone age, diagnosis of Turner syndrome.
- Baseline antibody testing (anti-growth hormone antibody screening assay (ATA), anti-growth hormone neutralizing antibody assay (Nab) and anti-growth hormone antibody binding capacity assay (ABC).
- Medical history in specific categories.
- Historical Laboratory Results on GH stimulation test (maximum GH level, insulin level, L-Dopa level), thyroid function test (free T4, total T4, TSH) in 12 months prior to informed consent/assent.
- Screening/Baseline physical examination results, including presence of hip or knee pain, fundoscopic examination and appearance of spine.

Subject listings on demographics, baseline characteristics, medical history, screening physical examination and historical laboratory measurements will be provided.

4.4 OUTCOME ANALYSES

Outcome analyses will be performed on the modified ITT population. In the analyses related to growth attenuation, growth velocity and height SDS, patients who enter puberty during the study period will be included only up to the last visit at which they were determined to be prepubertal.

The study windows listed below in Table 2 (based on visit dates) will be used:

Visit	Target Day	Window
Screening/Baseline	Day -28 to -1	Day -28 to 1
Month 1	Day 30	Day 2 to 60
Month 3	Day 90	Day 61 to 135
Month 6	Day 180	Day 136 to 225
Month 9	Day 270	Day 226 to 315
Month 12	Day 360	Day 316 to 405

Table 2 Study Windows

If more than one assessment is measured within the same visit window, then the record with the latest visit date (from baseline) will be used for that visit window.

Nutropin AQ (Somatropin [rDNA origin])—Genentech, Inc. 8/Statistical Analysis Plan ML29543

4.4.1 Primary Outcomes Endpoint

The primary endpoint for this study is the proportion of patients who develop anti-GH antibodies (i.e., with positive anti-GH antibody screening assay result) after initiating treatment with Nutropin AQ v1.1.

Among all patients with at least one post-baseline screening assay result, the number and percentage of patients who have at least one positive anti-GH antibody screening assay result at any post-baseline visit will be presented. The Clopper-Pearson exact 95% Cls for the percentage will also be provided.

An anti-GH antibody screening assay result is considered positive if the titer is \geq 1.0 mg/L.

4.4.2 Secondary Outcomes Endpoints

The secondary endpoints for this study are as follows:

- Proportion of patients who exhibit growth attenuation is defined as
 - (1) initial growth response greater than pretreatment velocity followed by reduction in growth response to below the pretreatment velocity in the subsequent 6- to 12month treatment period

or

(2) reaching \leq 2 cm per year at any scheduled visit: Month 3, 6, 9, or 12

Please note that for criteria (1), the initial growth response occurs as early as Month 3 and growth attenuation status at post-baseline visit will be evaluated at Months 6, 9, or 12.

The growth response is based on the annualized growth velocity defined as (height - baseline height)/ (date of height assessment – date of baseline)*365.25 at any post-baseline visit.

Pretreatment growth velocity is defined as (Baseline height – last historical height) / (date of baseline – date of last historical height)*365.25

Growth attenuation status at post-baseline visit Tk (=Month 6, Month 9 or Month 12 for k=6, 9, or 12) will be classified as follows:

Yes: If growth velocity at Tk< pretreatment growth velocity and there is Tj < Tk with growth velocity at Tj > pre-treatment growth velocity, for j<k, and k=6, 9, or 12 or growth velocity \leq 2 cm per year at any scheduled visit: Month 3, 6, 9, or 12 **No:** Otherwise.

Nutropin AQ (Somatropin [rDNA origin])—Genentech, Inc. 9/Statistical Analysis Plan ML29543 • 2x2 cross tabulation (with frequencies and percentages) of growth attenuation status (yes or no) and anti-GH antibody status (positive or negative) will be provided for each antibody assay at each visit (Month 6, 9, and12).

Similar tables of growth attenuation status (yes at any visit from Month 6 to Month 12) and anti-GH antibody status for those who had a positive antibody assay at any follow-up visit (negative at baseline) and those who remained negative throughout the study (including baseline) will also be provided.

- Proportion of patients with neutralizing anti-GH antibody (Nab positive) among those who had positive anti-GH antibody. This analysis will be summarized by visit, as well as cumulatively, for patients who had detectible anti-GH antibody (ATA) at any post baseline visit (with negative antibody assay at baseline), as well as those who remained negative throughout the study (including baseline).
- Annualized 6- to 12- month growth velocities and height SDS. These variables will be summarized separately for patients who were anti-GH antibody-positive at any post-baseline follow-up visit (negative at baseline) and those who were anti-GH antibody-negative at all visits (including baseline).

The difference between the annualized 6- and 12- month growth velocities will be presented separately for patients who were anti-GH antibody-positive at any post-baseline visit and those who were anti-GH antibody-negative at all visits (including baseline).

Graphic displays of the individual patient growth patterns (growth velocity); along with the longitudinal antibody profile over the course of the study will be prepared.

For the above analyses, if there is any patient who appears to have positive anti-GH antibody at baseline, they will be summarized separately from the other groups.

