6.3.1 Primary Endpoint

The primary endpoint for this study is the proportion of patients who develop anti-GH antibodies after *initiating* treatment with Nutropin AQ v1.1.

6.3.2 Secondary Endpoints

The secondary endpoints for this study are as follows:

- Proportion of patients who exhibit growth attenuation (defined as initial growth response greater than pretreatment velocity followed by reduction in growth response to below the pretreatment velocity in the subsequent 6- to 12-month treatment period or reaching ≤2 cm per year)
 - Cross tabulation between growth attenuation status (i.e., with or without) and anti-GH antibody status (i.e., positive or negative) will be provided for any

Nutropin AQ (Somatropin [rDNA origin])—Genentech, Inc.

48/Protocol ML29543, Version 2

antibody and for neutralizing anti-GH antibody, respectively, at each visit. Similar tables will also be provided for patients who had at least one positive anti-GH antibody (anti-GH antibody and neutralizing antibody, respectively) at any follow-up visit against those who never developed antibody after treatment.

- Proportion of patients with neutralizing antibody among those who had positive anti-GH antibody
 - This analysis will be summarized by visit, as well as *cumulatively*, for patients who had detectible anti-GH antibody at any post-baseline visit, as well as those who *remained negative throughout the study*.
- Annualized 6- and 12-month growth velocities and height SDS will be summarized separately for patients who were anti-GH antibody-positive at any post-baseline follow-up visit and those who were anti-GH antibody-negative at all visits (including baseline). Graphic displays of the individual patient growth patterns along with the longitudinal antibody profile over the course of the study will be prepared. Patients who enter puberty during the study period will be included up to the last visit at which they were determined to be prepubertal.

Additional analyses deemed appropriate for assessing immunogenicity will be described in the Statistical Analysis Plan.

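### The SAP 4.4.1 primary rule for patients who develop anti-GH antibodies has no baseline-negative condition, although three analyses in 4.4.2 have one (minor; the effect may be nil)

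*SAP*

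**What the plan says.** **Primary endpoint (SAP 4.4.1).** The endpoint concerns patients who develop antibodies, and the SAP explains that term as "i.e., with positive anti-GH antibody screening assay result) after initiating treatment with Nutropin AQ v1.1". The count is "Among all patients with at least one post-baseline screening assay result, the number and percentage of patients who have at least one positive" result at any visit after baseline. A result is positive at a titer of 1.0 mg/L or more, and the percentage gets a Clopper-Pearson 95% interval. Neither the numerator, the denominator nor the modified ITT definition (SAP 4.1.5) mentions baseline antibody status or a rise in titer.

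**Secondary endpoints (SAP 4.4.2).** Three analyses require a negative baseline for the positive group:

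- the cumulative growth-attenuation table: "anti-GH antibody status for those who had a positive antibody assay at any follow-up visit (negative at baseline";
- the neutralizing-antibody proportion: "at any post baseline visit (with negative antibody assay at baseline";
- growth velocity and height SDS: "anti-GH antibody-positive at any post-baseline follow-up visit (negative at baseline".

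Two other analyses in 4.4.2 do not state the condition: the by-visit 2x2 tables and the difference between 6- and 12-month velocities. The section closes with "For the above analyses, if there is any patient who appears to have positive anti-GH antibody at baseline, they will be summarized separately" from the remaining groups.

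**Protocol 6.3.2.** The corresponding groups are "anti-GH antibody-positive at any post-baseline follow-up visit and those who were anti-GH antibody-negative at all visits (including baseline". A negative baseline is required of the negative group only, so the condition on the positive group was added by the SAP.

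**The concern.** To develop antibodies after starting treatment is, on its ordinary meaning, to be without them beforehand. The counting rule does not require that. In three places the SAP treats baseline-positive children as a separate case, but it does not clearly do so for its main result. The number of positives in the primary table could then exceed the size of the positive group in the secondary tables, with no explanation in the plan.

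This is the only endpoint in the visible SAP that gets a confidence interval. Protocol 3.3.3 says the data will be used to judge whether the immunogenicity profile of the new-process product differs from that of the original. A child who was positive before exposure, and whose titer does not change, says little about that. A child whose titer rises on treatment is relevant, and the rule as written does not distinguish the two.

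**Working it through.** **1. The plan's own figures.** SAP 2.3, Table 1 gives Clopper-Pearson 95% limits. With x positives out of n, the lower limit is the 0.025 quantile of Beta(x, n−x+1) and the upper limit is the 0.975 quantile of Beta(x+1, n−x).

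| x/n | Recomputed | Printed |
|---|---|---|
| 25/50 | 0.3553–0.6447 | 0.3553–0.6447 |
| 30/60 | 0.3681–0.6319 | 0.3681–0.6319 |
| 10/50 | 0.1003–0.3372 | 0.1003–0.3372 |
| 12/60 | 0.1078–0.3233 | 0.1078–0.3230 |

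Three rows match exactly. The last upper limit differs by 0.0003, which does not affect this point.

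**2. Inputs for the illustration.**

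- N = 80 is the enrolment target and N = 50 the minimum evaluable number (SAP 2.3).
- Rates of 50% and 20% are the planning rates in SAP 2.3. The 10% rate is my assumption, to show a lower case.
- One child positive at baseline and again later is also an assumption. The documents give no baseline-positive rate.

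**3. Formula.** Let e = N × rate be the positives among baseline-negative children. The rule as written gives (e+1)/N. Restriction to baseline-negatives gives e/(N−1). The difference is [1 − e/(N−1)]/N. For N=80 and e=16 this is (1 − 16/79)/80 = 1.0 point.

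| N | Rate | As written (95% CI) | Baseline-negative only (95% CI) | Shift, points |
|---|---|---|---|---|
| 80 | 50% | 41/80 = 51.25% (39.8–62.6) | 40/79 = 50.6% (39.1–62.1) | 0.6 |
| 80 | 20% | 17/80 = 21.25% (12.9–31.8) | 16/79 = 20.3% (12.0–30.8) | 1.0 |
| 80 | 10% | 9/80 = 11.25% (5.3–20.3) | 8/79 = 10.1% (4.5–19.0) | 1.1 |
| 50 | 50% | 26/50 = 52.0% (37.4–66.3) | 25/49 = 51.0% (36.3–65.6) | 1.0 |
| 50 | 20% | 11/50 = 22.0% (11.5–36.0) | 10/49 = 20.4% (10.2–34.3) | 1.6 |
| 50 | 10% | 6/50 = 12.0% (4.5–24.3) | 5/49 = 10.2% (3.4–22.2) | 1.8 |

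The as-written half-widths are 7.5–11.4 points at N=80 and 9.9–14.5 at N=50, so one child's shift is small beside them.

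**4. More than one child.** Hold the as-written count at 10/50 = 20.0% (10.0–33.7). If one of the ten was positive at baseline, the restricted rate is 9/49 = 18.4% (8.8–32.0). If five were, it is 5/45 = 11.1% (3.7–24.1). From 25/50 = 50.0%, five such children give 20/45 = 44.4% (29.6–60.0). With none, nothing changes.

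**5. Direction.** Baseline-positive children who stay positive raise the as-written rate above the rate in baseline-negatives. A baseline-positive child who turns negative only enlarges the denominator and lowers it slightly, for example 10/50 = 20.0% against 10/49 = 20.4%.

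**6. Reach of the closing sentence of 4.4.2.** It stands at the end of 4.4.2, after analyses split by antibody group, and it separates baseline-positive patients from the other groups. It therefore appears to cover the two 4.4.2 analyses that lack the explicit condition. The primary analysis is one overall proportion with no groups and a denominator stated as all patients with a post-baseline result. The sentence does not clearly reach it, and it gives no revised numerator or denominator.

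**The case against.** The strongest reply is that nothing is left open. SAP 4.4.1 states its numerator, denominator, cutoff and interval, and its parenthesis defines what developing antibodies means in this study. That stands. A reader might infer that the plan fails to name its headline rate, but it does name one. The issue is whether that rate fits the endpoint's name and the SAP's own secondary groups.

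A reader might also infer that the SAP departs from the Protocol. It does not: the Protocol puts no baseline condition on its positive groups, and its primary endpoint states no counting rule. The unevenness lies inside the SAP.

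It can be argued that the closing sentence of 4.4.2 governs all of section 4.4. Its position before 4.4.3 allows that reading. Its place within 4.4.2 and its reference to other groups favour the narrower one.

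Nor is the restricted rate better in every respect. It would be too strong to say that pre-dose antibodies have no bearing on the product question, because a baseline-positive child whose titer rises on treatment is informative, and simple exclusion would hide that child. SAP 2.3 also wants enough patients to compare with earlier immunogenicity studies. The documents do not say how those studies counted, so restriction could help or harm comparability. Both points are reasons to keep the all-patients rate and show titers over time.

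Finally, the practical effect may be nil. Previous rhGH treatment is an exclusion (Protocol 4.1.2), no hypothesis test is planned (SAP 4), baseline antibody status is summarized (Protocol 6.2, SAP 4.3), and assay results are listed by patient and visit (SAP 4.6.3). All of this stands and limits the point to a minor one.

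**Conclusion.** The point holds as a minor inconsistency within the SAP and a cheap improvement. The primary rule counts a child who was positive before the first dose and again later, while three analyses in 4.4.2 keep such a child out of the positive group.

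On the assumption of one persistently positive child, the rate rises by 0.6–1.1 points at N=80 and 1.0–1.8 at N=50, well inside the interval. The documents do not give the number of such children, and it may be zero. They therefore do not support a claim that the primary rate will be materially inflated, and no planned test depends on it.

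One limit applies. The SAP text between 4.4.3 and 4.5 was not available, and the contents list shows a section 4.4.4, so the conclusion covers the visible text only.

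**What to change.** In SAP 4.4.1:

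- Make the denominator patients with a negative baseline screening result and at least one post-baseline result. Make the numerator those among them with at least one post-baseline positive.
- Report baseline-positive patients separately, with titers over time, so that any rise on treatment is visible.
- Place patients with a missing baseline result in the supportive analysis.
- Keep the rate among all patients, counting any post-baseline positive, as that supportive line. It preserves comparability if the earlier studies counted that way.
- State that the closing sentence of 4.4.2 applies to 4.4.1.

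The cost is SAP wording only, because the schedule of assessments already includes a baseline immunogenicity sample. The primary denominator falls by the number of baseline-positive or missing-baseline patients, for example from 80 to 79 with one.
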